İZMİR KÂTİP ÇELEBİ UNIVERSITY
INTERVENTIONAL CLINICAL STUDIES INSTITUTIONAL REVIEW BOARD

To: Asst. [name] [name], PhD

From: Assoc. [name] [name], MD, Chair

Date: 22.05.2025

IRB#:59

Study Title: A Comparative Clinical Evaluation of Two Resin-Based Fissure Sealants Applied with Different Isolation Techniques: An 18-Month Follow –Up Study

At its board meeting on 22.05.2025 your submission for the above referenced research study has received review and approval from İzmir Katip Çelebi Interventional Clinical Studies Institutional Review Board.

A handwritten signature in blue ink, appearing to read '[name]', is placed here.

Assoc. [name] [name]
Chair

Study Protocol with Statistical Analysis Plan, Informed Consent Forms, Ethical Approval

Materials and Method

Study Design

The randomized, controlled, single-blind study was approved by the Medical Ethics Committee of Izmir Katip Celebi University (approval number: 2025/059). Prior to the initiation of treatment, written informed consent was obtained from the parents of the children participating in the study. The study was conducted in accordance with the CONSORT (Consolidated Standards of Reporting Trials) guidelines to ensure transparent and comprehensive reporting of the clinical trial methodology and findings.

Sample Size

The estimation of sample size was conducted utilizing G*Power 3.1.9.7 software (Germany). According to the statistical parameters reported in a reference study,²² the effect size was set at 0.56, the alpha error at 0.05, and the power of the study at 0.81. It was determined that, in consideration of the established parameters, the minimum requisite sample size was to be calculated as 43 teeth per group. However, to account for an estimated loss of 20 of participants, which is a common occurrence in pediatric clinical studies due to factors such as non-compliance, anxiety, or missed follow-up appointments, the target sample size was adjusted to 50 teeth per group. Consequently, a total of 200 teeth (100 teeth per material and 50 teeth for four subgroups) was established to ensure sufficient statistical power and maintain the validity of the study despite potential participant loss.

Sample Inclusion and Exclusion Criteria

The study comprised 100 healthy children aged between 6 and 12 years, with a mean age of 7.9 years, ASA class I (American Society of Anesthesiologists), who were determined to exhibit cooperative behavior with a score of 3 or 4 on the Frankl Behavior Rating Scale. All participants had fully erupted lower first permanent molars on both sides (200 teeth), which

required the application of pit and fissure sealants. The inclusion criteria were based on the International Caries Detection and Assessment System II (ICDAS II) criteria, including deep and retained pits and fissures, no restorations, and no evidence of caries lesions. Participants with special needs or systemic disease (ASA classification II or higher), requiring emergency dental care, suffering from a severe gag reflex or an allergy to latex, exhibiting uncooperative behavior (Frankl Score 1 or 2), exhibiting molars with anomalies of the enamel/dentin, or unable to attend follow-up appointments were excluded from the study.

Screening Participants

The clinical phase of the study was conducted by two researchers. One was responsible for examination and treatment procedures, while the other (who was blinded) was responsible for follow-up procedures. The training process was repeated at 20 randomly selected sites until examiners demonstrated substantial correlation, as measured by Cohen's Kappa ($k \geq 0.7$). After the training of the examiners, the study was initiated. The first operator, who had undergone training and performed the evaluation of the presence of caries using visual examination methods following ICDAS criteria, screened 178 children to determine their eligibility. The health history and demographics of each participant were obtained, and a clinical examination was carried out. The latter was performed with the aid of a blunt instrument and a mouth mirror, the first mandibular molars selected for inclusion in this study were examined using radiography, with the objective of ruling out the presence of any signs of dental caries. This examination involved the analysis of bitewing radiographs, which were taken from both the right and left sides of each patient. In addition, a caries risk assessment was performed on the patients to be included in the study using the Cariogram programme (CarEng, version 3.0, Malmö University, Sweden). The following factors were taken into consideration during the evaluation process: caries experience (DMFT/DMFS values, new caries in the last year, number of fillings and missing teeth); systemic diseases; dietary content (especially sugar

consumption); number of daily meals and snacks; Silness-Löe Plaque Index scores; Streptococcus mutans level in saliva (by strip test); fluoride exposure information; salivary flow rate (by stimulated saliva test); and salivary buffer capacity (by Saliva-Check Buffer or strip tests). All data were entered into the Cariogram programme, which created a caries risk profile for each patient. Patients with moderate caries risk were included in the study. Participants who met the inclusion criteria were enrolled in the study after obtaining consent from their parents or legal guardians and assent from the participants themselves.

Blinding and randomization

A split-mouth study design was employed, whereby two different fissure sealant materials were applied using two different isolation techniques. Each patient received both sealants, with one applied under rubber dam isolation and the other under cotton roll isolation. The allocation of materials and isolation methods to specific teeth was randomized to minimize bias. A computer-generated randomized list *Research Randomizer (Ver;4.0)* was employed to determine the sequence of application of fissure sealant materials, as well as the side (right or left mandibular molar) on which each material would be applied. In accordance with the sealant material and isolation protocol, this randomized process resulted in the formation of four different study groups.

- (a) a highly filled fluoride-containing fissure sealant with rubber dam isolation,
- (b) a highly filled fluoride-containing fissure sealant with cotton roll isolation,
- (c) an unfilled fluoride-containing fissure sealant with rubber dam isolation,
- (d) an unfilled fluoride-containing fissure sealant with cotton roll isolation.

The chemical composition, manufacturer, and application procedures of the tested fissure sealant materials are shown in Table 1.

Clinical Procedure

The plaque and debris were removed from the occlusal surfaces using a rotating brush and non-fluoride prophylactic paste. In accordance with the results of the randomization process and following the determination of the materials and isolation methods to be employed on each side of the patient, each tooth was isolated using a rubber dam, an arch and metal clasps, or cotton rolls with a high-volume suction, to avoid contamination from saliva. The application was carried out under proper illumination in accordance with the manufacturers' recommendations, as outlined in Table 1. Following the successful application of the designated sealant to the first tooth, the contralateral homologous tooth was sealed using an alternative material. The polymerisation of all materials was conducted using an LED light-curing unit (Valo, Ultradent Products Inc., South Jordan, Utah, USA), in accordance with the manufacturer's instructions. After each application, the sealant was subjected to testing for the absence of air bubbles, marginal adaptation, retention, and complete polymerisation. If a deficiency was identified, the tooth was re-treated. The occlusion was then subjected to evaluation, with any potential premature contacts being eliminated. All children were provided with oral hygiene instructions and any other necessary dental treatment.

Follow-up

The evaluation of pit-and-fissure sealants was conducted to record the presence of caries lesions and sealant retention at 6-, 12-, and 18-month follow-up visits. The evaluation was performed by one calibrated pediatric dentist, who was unaware of which sealant had been used and the teeth were air-dried and observed under appropriate illumination following toothbrush prophylaxis. The International Caries Detection and Assessment System (ICDAS) II criteria were employed to record caries lesions and following classification system was employed for the retention evaluation of the sealants: 1 = complete retention; 2 = partial loss; or 3 = complete loss. The pit-and-fissure sealants that were noted to have undergone complete loss during the

follow-up appointments were subjected to re-treatment, exclusion from the study, and documentation as complete loss until the conclusion of the follow-up period.

Statistical Analysis

The analysis of the retention rates of the fissure sealant materials was conducted utilizing the IBM SPSS Statistics 30.0 statistical software package (SPSS, Chicago, Illinois, USA). Chi-square tests were used to determine whether there were statistically significant differences in retention rates between sealant materials and isolation techniques at different time points at the five percent significance level. The Kaplan-Meier survival analysis was applied to assess the cumulative retention rates of the sealants over time. The Log-Rank test was utilized to compare the survival distributions between different groups. The median and mean survival times for each fissure sealant and isolation technique were calculated, along with their 95% confidence intervals (CI).

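### 43 teeth per group at power 0.81 does not follow from any two-sided 5% calculation with 0.56 as d or h; on those readings, power between two independent subgroups is about 0.71 to 0.75

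*Combined protocol and SAP*

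**What the plan says.** The Sample Size section reports a G*Power calculation based on a reference study: "the effect size was set at 0.56, the alpha error at 0.05, and the power of the study at 0.81". From this, "the minimum requisite sample size was to be calculated as 43 teeth per group". The figure is raised to 50 per group for loss, giving "a total of 200 teeth (100 teeth per material and 50 teeth for four subgroups"). The metric behind 0.56, the test, the number of tails and the comparison being powered are not given.

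The Blinding and randomization section defines four groups: filled sealant with rubber dam (a), filled with cotton roll (b), unfilled with rubber dam (c) and unfilled with cotton roll (d). It adds: "Each patient received both sealants, with one applied under rubber dam isolation and the other under cotton roll isolation".

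The Statistical Analysis section states: "Chi-square tests were used to determine whether there were statistically significant differences in retention rates between sealant materials and isolation techniques", at several time points and "at the five percent significance level". It also says: "The Log-Rank test was utilized to compare the survival distributions between different groups". No directional hypothesis and no rank-sum test appear anywhere.

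**The concern.** The 43 and the 50 are set per subgroup, so 0.81 reads as the power for comparing two subgroups with the planned tests. Those tests look for a difference in either direction at 5%. A one-sided 5% calculation has the power of a two-sided 10% test, so a one-sided figure carried over to them would be too high.

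At stake is how a null result between two subgroups is read. The plan implies a 19% chance of missing the assumed effect (1 − 0.81). Under h with the chi-square test the chance is 25 to 27%. Under d it is 27% (t) or 29% (rank-sum).

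**Working it through.** **Inputs.** Effect size 0.56, alpha 0.05, power 0.81 and 43 per group come from the Sample Size section. Non-directional tests at 5% come from the Statistical Analysis section. Retention rates, baselines and hazard shape are assumptions, because the documents give none.

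**1. The plan's own figure, two-sided 5%.** Under h, n per group = 2 × ((1.960 + 0.878) / 0.56)² = 51.4, so 52. Under d with noncentral-t power, 52 gives 0.807 and 53 gives 0.815, so 53. For the rank-sum test (efficiency 3/π), 54 gives 0.804 and 55 gives 0.811, so 55. None gives 43.

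**2. The closest match found.** One-sided 5% rank-sum test, d = 0.56:
- At 43, effective n = 43 × 3/π = 41.06 and noncentrality = 0.56 × √(41.06/2) = 2.537. With critical value 1.664 on 80.1 df, power is 0.808.
- At 42, power is 0.7999. At 44 it is 0.816.

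So 43 is the smallest n for a target of 0.80, and its achieved power rounds to 0.81. Against a target of 0.81 the same test needs 44. The one-sided t-test reaches 0.80 at 41 (0.808), and one-sided h at 40 (0.805).

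**3. Two-sided 5% power for two independent groups.** Under h by normal approximation at 43: Φ(0.56 × √(43/2) − 1.960) = Φ(0.637) = 0.738.

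| Reading and test | 43 v 43 | 50 v 50 | 86 v 86 |
|---|---|---|---|
| h, Pearson chi-square, exact enumeration | 0.725–0.752 | 0.796–0.816 | 0.955–0.962 |
| h, log-rank, simulated | 0.731–0.760 | 0.793–0.818 | 0.957–0.964 |
| d, t-test | 0.728 | 0.792 | 0.955 |
| d, rank-sum | 0.708 | 0.773 | 0.946 |

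The chi-square and log-rank rows assume 30 to 75% retention in the lower group, for example 0.50 v 0.766. The log-rank row uses 100,000 runs per point, constant hazard, visits at 6, 12 and 18 months and no other censoring.

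The h-based chi-square figure does not carry over to d. If d is the standardised difference of the retained/not-retained indicator, exact chi-square power at 43 is 0.70 to 0.79. If d is a shift on an underlying normal scale that is then dichotomised, it is about 0.32 to 0.55.

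**4. Which comparisons this covers.** A child's two teeth differ in both factors, so each child carries a and d, or b and c. The four pairs that change one factor (a–b, c–d, a–c, b–d) therefore compare different children, and independent-group power applies. Pairs a–d and b–c are within-child and are not covered. Pooled material and isolation contrasts use 2 × 43 = 86 teeth a side; the 86 v 86 column ignores their pairing.

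**5. Other readings of 0.56.**
- w: 26 teeth in total for 0.81 at 1 df, and 45 in total at 6 df.
- f with four groups: 40 teeth in total.
- dz: 28 pairs.
- Relative risk, exact chi-square at 43 v 43: 0.58 at baseline 0.50, 0.81 at about 0.69, 0.94 at 0.80.
- Hazard ratio: 96 events for 0.81, more than the 86 teeth in two subgroups.

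**The case against.** The strongest reply is that the documents never call the calculation one-sided. The match needs a target of 0.80, whereas the section says power was set at 0.81. It is also sensitive to rounding: at d = 0.555, 43 per group gives 0.802, and at d = 0.5649, 42 already gives 0.806. The metric sits in a reference study that the documents do not reproduce. For a chi-square test, w is a natural effect size, and under w the trial is over-sized. All of this stands. A reader might infer that the sponsor ran a one-sided test; the documents do not establish it.

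A second reply is that the Statistical Analysis section names chi-square for materials and isolation techniques, which are pooled contrasts with about 0.95, and leaves the groups in the log-rank test unspecified. This also stands. A reader might infer that the whole trial is under-powered, but the figures do not support that. At the target of 50 before any loss, chi-square power under h is 0.80 to 0.82, about the stated value.

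The reply does not rescue the printed pair. No two-sided calculation with d, h, w, f or dz yields 43 per group at 0.81. Of the readings tried, only a relative risk with an assumed baseline near 0.69 does so.

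**Conclusion.** The point holds conditionally and should be fixed. With 0.56 as d or h, 43 per group at 0.81 is inconsistent with the planned non-directional tests. For two independent subgroups of 43, power is about 0.73 to 0.75 by chi-square if 0.56 is h, and 0.73 (t) or 0.71 (rank-sum) if it is d. It could be lower by chi-square if d is a shift on an underlying scale.

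One-sidedness is the best available explanation, not an established fact. The shortfall disappears if 0.56 is w, f or dz. If it is a relative risk, power equals 0.81 only at a baseline near 0.69, and is lower below that and higher above it. The consequence is limited to pairwise comparisons of independent subgroups. Confidence is medium, because the metric has to be inferred.

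**What to change.** In the Sample Size section, name the metric (taken from the reference study), the test, the sidedness and the comparison behind the 43. Recompute power at 43 per group for the planned two-sided test, and replace 0.81 with that figure for subgroup comparisons: about 0.73 to 0.75 under h, or 0.71 to 0.73 under d by t or rank-sum. Under d, a chi-square figure also needs the assumed retention proportions.

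If 0.56 is a relative risk, give the baseline; 0.81 may then stand. If it is w, f or dz, say so and note the over-sizing. State power for the pooled material and isolation contrasts separately, and make any power quoted for within-child contrasts (including a–d and b–c) match the analysis actually used.

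The cost is one paragraph of text with no change to enrolment. The only downside is a less favourable stated power for subgroup comparisons.

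### Fifty teeth per group does not cover the assumed loss of 20 in 100: it leaves 40, below the plan's own minimum of 43

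*Combined protocol and SAP*

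**What the plan says.** Everything at issue is in one paragraph, the Sample Size section of the combined protocol and SAP.

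- Design values: "the effect size was set at 0.56", "the alpha error at 0.05" and "the power of the study at 0.81".
- Base requirement: "the minimum requisite sample size was to be calculated as 43 teeth per group".
- Allowance: "to account for an estimated loss of 20 of participants", "the target sample size was adjusted to 50 teeth per group". No per cent sign is printed after the 20.
- Result: "a total of 200 teeth (100 teeth per material and 50 teeth for four subgroups"), a number that "was established to ensure sufficient statistical power and maintain the validity of the study despite potential participant loss".

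Two other sections fix how lost children turn into lost teeth. Sample Inclusion and Exclusion Criteria gives 100 children and 200 teeth. Blinding and randomization says that each child receives both sealants, one under rubber dam and the other under cotton rolls, so each child contributes one tooth to each of two groups. No other section gives a different loss rate or a further allowance.

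**The concern.** A loss allowance should leave at least the required number once the assumed loss has happened. Here the step from 43 to 50 is too small for the loss it is meant to absorb, yet the section concludes that power is protected. Someone judging whether a non-significant 18-month comparison between subgroups is informative would rely on that conclusion. The section on study design also commits the trial to CONSORT reporting, so the sentence is likely to be carried into the published sample-size statement.

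**Working it through.** **Inputs.** Minimum 43 teeth per group, target 50 per group in four groups (200 teeth), loss of 20 (all from Sample Size). 100 children with two study teeth each (Sample Inclusion and Exclusion Criteria; Blinding and randomization).

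**1. The plan's base figure of 43.** The type of effect size, the test and the sidedness are not stated. Assume that 0.56 is a standardised difference between two independent groups. Power is then the upper tail of a noncentral t distribution with df = 2m - 2 and noncentrality 0.56 x sqrt(m/2), where m = n for the t-test and m = 3n/pi for the rank-sum test. For the one-sided rank-sum test at n = 43, m = 41.06, the noncentrality is 2.537 and power is 0.808, which rounds to the stated 0.81. So 43 is reproduced, but only one-sided. Two-sided, 0.81 power needs 52 (normal approximation), 53 (t) or 55 (rank-sum). That is a separate matter; 43 is taken as given from here on.

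**2. The allowance.**

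| Calculation | Result |
|---|---|
| Needed to keep 43 after 20% loss: 43/(1 - 0.20) = 53.75 | 54 per group (216 teeth, 108 children) |
| Incorrect shortcut: 43 x 1.2 = 51.6 | 52 per group |
| Plan's target | 50 per group (200 teeth, 100 children) |
| Left from 50 after 20% loss: 50 x 0.80 | 40 per group (160 teeth, against 4 x 43 = 172) |
| Largest loss that 50 can absorb: 1 - 43/50 | 14% |

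Neither formula gives 50.

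**3. Reading the text as 20 children.** 20 children x 2 teeth = 40 teeth lost; (200 - 40)/4 = 40 per group on average. An uneven split does not help. Under the allocation rule a child contributes either to groups (a) and (d) or to groups (b) and (c), so 50 teeth per group means 50 children of each kind. If 20 children are lost, at least one kind loses 10 or more, and at least two of the four groups end with 40 or fewer.

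**4. Chance variation.** If each child is retained independently with probability 0.80, the probability that a given group of 50 keeps at least 43 is 0.19.

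**5. Cost in power, on the assumption in step 1.**

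| Test | n = 43 | n = 40 |
|---|---|---|
| One-sided rank-sum (matches the stated 0.81) | 0.808 | 0.782 |
| One-sided t | 0.824 | 0.799 |
| Two-sided t | 0.728 | 0.696 |
| Two-sided rank-sum | 0.708 | 0.676 |

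Like for like, the shortfall costs about 2.5 to 3 percentage points. The lower two-sided values come mostly from sidedness and should not be charged to the loss allowance.

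**The case against.** - **The plan does not literally say 20%.** True; the per cent sign is an inference. With 100 children the two natural readings coincide. Only a loss of 20 teeth in total would leave (200 - 20)/4 = 45 per group, and the text counts participants.
- **The documents do not identify a power at 40 per group.** This stands. Statistical Analysis plans chi-square and log-rank tests, not a t or rank-sum test. Were 0.56 a chi-square effect size w, power for two groups of 40 would exceed 0.99, though that reading does not reproduce 43 per group. The power values are therefore illustrative. The comparison of 40 with 43 uses none of them.
- **Children lost late still contribute.** Partly right. They add censored time to the Kaplan-Meier and log-rank analyses and count in the chi-square tests at the visits they attended. They are missing from the 18-month chi-square comparison, and the stated minimum is expressed in teeth, with no credit for partial follow-up. The Follow-up rule that carries complete sealant loss forward covers outcomes, not children who stop attending.
- **Comparisons pooled over material or isolation have more teeth.** Also right: 100 per material becomes 80 after the loss. But the plan attaches both 43 and 50 to the four subgroups, and those are where its minimum is missed.
- **The shortfall is small and the children are already described as enrolled.** Agreed. This limits the remedy to correcting the statement; it does not make the statement true.

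**Conclusion.** The concern holds. At the loss the plan itself assumes, 50 teeth per group leaves an expected 40, three below its stated minimum in every subgroup, and the claim that 200 teeth protect power despite that loss is wrong as written. Fifty would be adequate for a loss of up to 14%.

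This conclusion needs only that the 20 means 20% or 20 of the 100 children. The estimate of the consequence, roughly 2.5 to 3 points of power, further assumes that 0.56 is a two-group standardised difference. The practical effect is modest, but the figure is one the trial relies on and it is cheap to correct.

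**What to change.** Correct the paragraph in Sample Size in one of two ways:

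1. State that 50 teeth per group maintains the minimum of 43 for losses of up to 14%; or
2. Keep the 20% assumption, state that 40 evaluable teeth per group are expected at 18 months, and give the power at 40, naming the effect-size type, the test and the sidedness used.

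In either case, restore the per cent sign (or say that 20 children are meant) and remove the claim that 200 teeth preserve the stated power under the assumed loss.

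The cost is one sentence and a slightly less favourable loss tolerance or power. No additional children need be enrolled and no analysis changes.

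### Material and isolation switch together within every child, and no planned analysis shows whether the sealant difference depends on isolation

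*Combined protocol and SAP*

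**What the plan says.** The study title announces "A Comparative Clinical Evaluation of Two Resin-Based Fissure Sealants Applied with Different Isolation Techniques". Under Blinding and randomization, "Each patient received both sealants, with one applied under rubber dam isolation and the other under cotton roll isolation"; the section adds that "The allocation of materials and isolation methods to specific teeth was randomized to minimize bias" and that "this randomized process resulted in the formation of four different study groups". The groups are the four combinations of filled or unfilled sealant with rubber dam or cotton rolls, lettered a to d as in the summary above. Clinical Procedure confirms that "the contralateral homologous tooth was sealed using an alternative material".

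On numbers, Sample Inclusion and Exclusion Criteria says "The study comprised 100 healthy children aged between 6 and 12 years", and Sample Size gives 200 teeth, 100 per material and 50 in each of the four subgroups.

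Statistical Analysis uses chi-square tests to determine "whether there were statistically significant differences in retention rates between sealant materials and isolation techniques at different time points". For the survival analysis it says only: "The Log-Rank test was utilized to compare the survival distributions between different groups". Survival times are to be summarised by sealant and isolation technique. The section names no model with both factors, no interaction, no comparison of materials within an isolation technique and no list of pairwise contrasts.

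**The concern.** Two sealants under two isolation techniques form a 2x2 factorial. A reader of this trial will want to know whether any sealant advantage holds under rubber dam, under cotton rolls, or both. The analysis section does not answer that on either reading of its wording.

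- **Read by factor**, each test pools one factor over the other. If isolation matters more for one sealant, the pooled result describes neither setting.
- **Read by cell**, an overall test of four groups is significant for any main effect and so does not isolate interaction. Pairwise tests would include a v d and b v c, which change material and isolation together, and nothing in the plan says how those two are to be read.

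Using the pairing would not by itself cure this: a paired test of pooled material still says nothing about dependence on isolation.

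**Working it through.** **1. The plan's own figure.** Sample Size gives effect size 0.56, alpha 0.05, power 0.81 and 43 teeth per group. For two independent groups, n = 2(z_alpha + z_power)²/d².
- One-sided: 2(1.645 + 0.878)²/0.56² = 40.6, so 41. The noncentral t gives 42 and the Wilcoxon-Mann-Whitney version 44.
- Two-sided: 2(1.960 + 0.878)²/0.56² = 51.4, so 52. The noncentral t gives 53.

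The figure of 43 is therefore close to a one-sided comparison of two independent groups (sidedness and type of effect size are not stated). It does not size an interaction.

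**2. The contrasts.** Fifty teeth per cell and 100 children imply 50 a+d children and 50 b+c children.

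| Contrast | Differs in | Children |
|---|---|---|
| a v b | isolation | different |
| c v d | isolation | different |
| a v c | material | different |
| b v d | material | different |
| a v d | both | same |
| b v c | both | same |

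**3. What can be estimated.** Material main effect = [(a−d) + (b−c)]/2. Isolation main effect = [(a−d) − (b−c)]/2. Both come from within-child differences and are orthogonal at 50/50. Interaction = (a−c) − (b−d) = (a+d) − (b+c), which compares the two types of child. The design matrix without child effects has rank 4, so all terms are estimable. With a fixed effect per child the rank stays at 102 when the interaction is added, so an analysis of within-child differences alone cannot estimate it.

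**4. Illustration.** The documents give no cell rates. Assume 18-month retention, taken as yes or no, of a 85%, b 80%, c 80%, d 50%.
- Pooled material: (85 + 80)/2 − (80 + 50)/2 = 82.5 − 65 = 17.5 points.
- Under rubber dam: a−c = 5. Under cotton rolls: b−d = 30.
- Within child: a−d = 35 and b−c = 0.
- Interaction: 5 − 30 = −25 points.

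A pooled test cannot detect this pattern as such. Rates of 90/70/80/60 (10 points under each technique) and 90/60/70/60 (20 points and 0) both give a pooled difference of 10.

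**5. Power of the planned pooled test.** The unpaired chi-square compares 100 with 100 teeth. Its null standard error is √(2 × 0.7375 × 0.2625/100) = 0.0622, so the difference must exceed 1.96 × 0.0622 = 0.122. The true standard error, simulated with a logistic child effect of SD 0, 1.8 and 3, is 0.059, 0.050 and 0.045. Power = Φ[(0.175 − 0.122)/SE] = about 82%, 86% and 88%. Simulation gives 82%, 86% and 89%. A test that uses the pairing would reach about 84%, 93% and 98%, but the plan does not name one.

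**6. Precision of the interaction.** With tooth variance s² and within-child correlation rho, Var(main) = s²(1 − rho)/50 and Var(interaction) = 4s²(1 + rho)/50. The ratio is 4(1 + rho)/(1 − rho):
- rho 0.3: 5.2/0.7 = 7.4
- rho 0.5: 6/0.5 = 12

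In the step 4 scenario the interaction of 0.25 has standard error 0.118, 0.134 and 0.140. Φ(0.25/SE − 1.96) gives about 56%, 46% and 43%; simulation gives 56%, 47% and 43%. For a standardised interaction of 0.56 (tooth SD 1), SE = √(4(1 + rho)/50), and two-sided power is 51%, 41%, 37% and 33% at rho 0, 0.3, 0.5 and 0.7.

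**The case against.** The strongest reply is that the plan never says each factor is pooled over the other. The log-rank sentence refers to groups, the randomization section uses that word for the four cells, and the sample size is set per cell. A four-cell analysis is a fair reading. The two harms also belong to opposite readings: a pooled-only analysis never computes a v d or b v c, and a full pairwise analysis would also compute a v c and b v d. No hypothesis about interaction is stated, main effects are a legitimate target, and the trial has little power for an interaction.

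Much of this stands. Pooling is the natural reading of the chi-square sentence, but not a stated one. The misattribution risk exists only if the cells are compared pairwise, and it remains a possibility because every group label carries both factors.

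A reader might infer that switching both factors together confounds material with isolation, or that the design cannot answer the question. The documents do not support that. At 50/50 the main effects are unconfounded, all four cells exist, and materials and isolation are both said to be randomized to teeth, so between-child contrasts remain randomized comparisons, only less precise.

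What the reply does not remove is that, on neither reading, does the section name an analysis of whether the sealant difference varies with isolation.

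**Conclusion.** The point holds as a gap in the analysis plan, not as a fault in the design, and should be put right. The a+d or b+c pairing follows directly from the text. So does the result that two of the six possible contrasts mix the factors and that these are the only within-child ones. Statistical Analysis names no two-factor model, interaction or material-within-isolation comparison.

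The size is illustrative. Under the assumed rates, a 17.5-point pooled advantage would usually be declared while the underlying differences are 5 and 30 points. The rates were chosen to show a strong interaction. The within-child correlation is not in the documents and is shown over a range. Power figures for retention are on the percentage-point scale, with no loss to follow-up.

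**What to change.** In Statistical Analysis, replace the separate chi-square comparisons with one retention model containing material, isolation and their product, with child as the cluster (for example GEE or a child random effect).

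- Report the two main effects, the material difference within each isolation technique (a v c, b v d) and the isolation difference within each material (a v b, c v d), all with 95% confidence intervals. State the scale, since interaction in percentage points and in odds ratios need not agree.
- State that a v d and b v c are not interpreted as material or isolation effects.
- State which groups the log-rank test compares.
- State that a non-significant interaction will not be read as absence of interaction.

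Covariate adjustment of the between-child contrasts is optional. The Cariogram score would add little, because Screening Participants admits only children at moderate risk.

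The cost is wording and one model; no new data or children are needed. The downside is real: the interaction has 7.4 to 12 times the variance of a main effect at rho 0.3 to 0.5, so its interval will be wide and may qualify a simple headline result.
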